6.3.3. FACIT-Fatigue

The FACIT-Fatigue questionnaire consists of 13 items scored on a 5-point Likert scale (0 = not at all, 4 = very much). The FACIT-Fatigue subscale scoring guideline (V 4) will be used as follows (<https://www.facit.org/measures/FACIT-Fatigue>):

- All negatively stated items (ie, all items except An5 and An7 from the eCRF) are to be reversed by subtracting the response from 4.
- After reversing the proper items, all items are summed to obtain a score.
- The Fatigue subscale score is then calculated by multiplying the sum of the item scores by 13, then dividing by the number of items answered.

When there are missing data, prorating by subscale in this way is acceptable as long as more than 50% of the items were answered. The score has a range of 0 to 52 with higher scores indicating better QoL.

6.4. Appendix 4: Additional Details on Statistical Methods

6.4.1. SAS Code for ANCOVA Analysis

The primary analysis of the primary endpoint utilizes ANCOVA analysis for evaluating the percentage change from baseline to Week 26 in proteinuria. Sample code is provided below:

Step 1: Impute data on or after receipt of additional standard-of-care therapy (LN cohort only) using the value collected at the time of renal flare or extrarenal SLE flare

Step 2: Impute data on or after treatment discontinuation using multiple imputation as described in Section 6.4.3.

Step 3: Analyze imputed datasets using ANCOVA analysis

```
proc glm data=ADEF;
  by _imputation_;
  class trt01pn strat;
  model chg= trt01pn base strat/ solution;
  lsmeans trt01pn / cl diff stderr;
run;
```

where trt01pn is the randomized treatment group, base is the log(proteinuria) value at baseline, strat is the randomization stratification variable and chg is the change from baseline in log(proteinuria).

Step 4: Inferences from each complete data set will be combined to obtain an overall test statistic for each treatment effect.

```
proc mianalyze data=diff2;
  by avisitn;
  modeleffects estimate;
  stderr;
run;
```

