2. STATISTICAL HYPOTHESES

The primary hypothesis for this study is that ravulizumab is superior to placebo in decreasing proteinuria. Hypothesis testing will be one-sided and performed at the 0.05 level of significance.

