5.3.2. Main Analytical Approach

The primary analysis of the primary efficacy endpoint (percentage change from baseline in proteinuria at Week 26) will be conducted for each disease-specific cohort after all participants have completed the protocol-required assessments in the Initial Evaluation Period.

For the primary efficacy endpoint, when two 24-hour urine collections are required and only 1 collection is available at the visit, then this value will be used for analysis. When more than 2 collections are available at the visit, only 2 valid collections recorded in the eCRF will be used for analysis.

To reduce skewness, the natural logarithm will be used to transform proteinuria values before analysis. An analysis of covariance (ANCOVA) will be used for the primary efficacy endpoint to compare reductions in proteinuria between the ravulizumab and placebo treatment groups. The ANCOVA model will include change from baseline in log-transformed proteinuria as the response variable and will adjust for baseline log proteinuria and the randomization stratification factor. The treatment effect will be evaluated using the least squares mean difference between treatment groups. The point estimate and 2-sided 90% confidence interval (CI) for the mean difference of log-transformed proteinuria will be back transformed (via exponentiation) to obtain the GMR and corresponding 2-sided 90% CI. The values will then be expressed as percentage change in adjusted geometric mean of proteinuria at Week 26 relative to baseline.

Data collected on or after receipt of additional standard-of-care therapy (for LN cohort) will be imputed using the proteinuria value from the 24-hour urine collection performed at the time of renal flare or extrarenal SLE flare. Data collected on or after treatment discontinuation will be assumed MAR and imputed using multiple imputation.

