6.4.3. SAS Code for Multiple Imputation

For the primary analysis of the primary endpoint, responses after treatment discontinuation will be imputed using a multiple imputation approach assuming the data are MAR and using a regression model. Sample code is provided below:

Step 1: Imputation using a monotone regression model at Week X

```
proc mi data=ADEF out=outmi seed=123 n impute=1000;  
  class trt01pn strat;  
  var trt01pn base strat Week26;  
  monotone reg(/details);  
run;
```

where trt01pn is the randomized treatment group, base is the log(proteinuria) value at baseline, strat is the randomization stratification variable, and Week 26 is the change from baseline in log(proteinuria) at Week 26.

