6.4.4. SAS Code for Placebo-based Imputation

A sensitivity analysis for the primary endpoint will be performed using placebo-based imputation for responses after treatment discontinuation. In this analysis, data occurring after treatment discontinuation will be set to missing and multiple imputation will then be performed, using a regression method obtained only from placebo-treated participants with terms for baseline value and the randomization stratification variable.

The following is a partial SAS code for the placebo-based pattern imputation at Week 26:

```
proc mi data=ADEF out=outmi seed=123 n impute=1000;  
  class trt01pn strat;  
  var base strat Week26;  
  monotone reg(/details);  
  mnar model (Week26/modelobs=(trt01pn='Placebo'));  
run;
```

where trt01pn is the randomized treatment group, base is the log(proteinuria) value at baseline, strat is the randomization stratification variable, and Week26 is the change from baseline in log(proteinuria) at Week 26.

The 1000 imputed data sets are then analyzed using ANCOVA (refer to Section 6.4.1 for the SAS code), and the PROC MIANALYZE procedure will be used to generate valid statistical inferences about these parameters.

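### The sample pooling code for the primary analysis gives no complete-data degrees of freedom; run as printed, the 90% interval would be about 1-2% too narrow and the one-sided level about 5.1-5.3%

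*SAP*

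**What the plan says.** - **Test and interval.** SAP 2: "Hypothesis testing will be one-sided and performed at the 0.05 level of significance". SAP 5.3.2 reports "The point estimate and 2-sided 90% confidence interval (CI) for the mean difference of log-transformed proteinuria", back-transformed to a geometric mean ratio.
- **Analysis model.** SAP 6.4.1 fits "model chg= trt01pn base strat/ solution" in PROC GLM to each imputed data set. SAP 6.4.3 creates those data sets with "proc mi data=ADEF out=outmi seed=123 n impute=1000".
- **Pooling.** The last step in 6.4.1 is "proc mianalyze data=diff2", with "modeleffects estimate" and the standard error. The call has neither EDF= nor ALPHA=. The code is introduced by "Sample code is provided below".
- **Reuse.** SAP 6.4.4 (placebo-based imputation) refers back to the 6.4.1 code and says that "the PROC MIANALYZE procedure will be used to generate valid statistical inferences about these parameters". SAP 6.4.5 (tipping point) says the same.
- **Degrees of freedom.** SAP 5.3.2, SAP Appendix 4 and Protocol 9.4.1.1 give no rule for the pooled primary test. The secondary MMRM does have one: Kenward-Roger, in SAP 5.4.1 and in the 6.4.2 code.

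**The concern.** PROC MIANALYZE can apply a small-sample correction only if it is told the degrees of freedom that the complete-data analysis would have had. Without EDF= it takes them as infinite and uses Rubin's value, which depends only on the number of imputations and the fraction of missing information. This is known behaviour of the procedure; the documents do not state it. With 1000 imputations Rubin's value is enormous.

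The same ANCOVA on complete data would use t with 56 degrees of freedom. Once data go missing and results are pooled as printed, the critical value falls, although less information should not tighten the reference distribution.

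At stake are the only formal test in each cohort, its interval, and the sensitivity analyses that reuse the code. SAP 5.3.3 defines the tipping point as the delta at which the two-sided p-value crosses 0.10, so the reported delta would shift slightly in ravulizumab's favour.

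**Working it through.** The plan gives no pooled degrees of freedom to reproduce, so the check compares what the printed call implies with what the model supports.

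**Inputs.** N = 60 per cohort, 40:20 (SAP 3); 4 model parameters, namely intercept, treatment, baseline and a two-level stratum (SAP 6.4.1); m = 1000 (SAP 6.4.3); one-sided 0.05 (SAP 2). The fraction of missing information, λ, is an assumption. The 10% dropout in SAP 3 is the guide, and 0-20% is the range.

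**Complete-data error degrees of freedom.** 60 − 4 = 56; t(0.95, 56) = 1.6725.

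**As printed (Rubin).** ν = (m − 1)/λ². At λ = 0.10: 999/0.01 = 99,900. At λ = 0.20: 999/0.04 = 24,975. Both give a critical value of 1.645.

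**With EDF = 56 (Barnard-Rubin).** ν_obs = (57/59) × 56 × (1 − λ).
- λ = 0.10: 54.10 × 0.90 = 48.69. Combined with 99,900 this is 48.67, critical value 1.677; 1.677/1.645 = 1.019.
- λ = 0.20: 54.10 × 0.80 = 43.28. Combined with 24,975 this is 43.2, critical value 1.681; 1.681/1.645 = 1.022.
- No missing data (limit): 1.6725/1.645 = 1.017. The tail of t(56) beyond 1.645 is 0.0528.

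**Allowing for the standard error.** Critical values alone overstate the problem, because regression imputation draws the residual variance and so inflates the pooled variance a little. Take 10% missing, equally by arm, with the imputation model equal to the analysis model, as 6.4.1 and 6.4.3 have it. Then 54 values are observed, with 54 − 4 = 50 degrees of freedom, and the drawn variance averages 50/48 = 1.0417 times the estimate. In units of the exact observed-data variance:
- within-imputation: [(50 + 6 × 1.0417)/56] × 0.90 = 0.9040
- between-imputation: 1.0417 × 0.10 = 0.1042
- total 1.0082, so the standard error is inflated by √1.0082 = 1.0041.

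The effective cut-off is 1.645 × 1.0041 = 1.652, against an exact t(0.95, 50) of 1.676. The interval is therefore about 1.5% too narrow, and the level is the tail of t(50) beyond 1.652, which is 5.24%. With EDF the cut-off is 1.677 × 1.0041 = 1.684 and the level 4.92%. The same steps at 20% missing (44 degrees of freedom, standard error inflated by 1.0088) give an interval 1.2% too narrow without EDF and 0.9% too wide with it.

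**One-sided level in %, without EDF / with EDF.**

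| Missing | Calculation above | Simulation, 40,000 trials (MC SE about 0.11) | Second simulation (MC SE about 0.16) |
|---|---|---|---|
| 0% | 5.28 / 5.00 | 5.15 / 4.87 | 5.3 / 5.0 |
| 5% | 5.26 / 4.96 | not run | 5.1 / 4.8 |
| 10% | 5.24 / 4.92 | 5.26 / 4.94 | 5.3 / 5.0 |
| 20% | 5.21 / 4.85 | 5.13 / 4.75 | 5.1 / 4.7 |

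A further 30,000 trials at 10% missing gave 5.32 / 4.96 (MC SE 0.13). In the 40,000-trial run at 10%, the nominal 90% interval covered 89.4% without EDF and 90.1% with it.

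**The case against.** The strongest reply is that this is sample code and plainly incomplete. In 6.4.1 the data set `diff2` is never created from the PROC GLM step, pooling is by a visit variable that the GLM step does not contain, and there is no ALPHA=0.1 although 5.3.2 fixes a 90% interval. If options were left out even where the text settles them, a missing EDF= says little about the final program. That stands. A reader might infer that the SAP has adopted a normal reference for the primary test. The documents do not support this: 5.3.2 is silent on the point, and the code is illustrative. What remains is that nothing in the SAP would lead a programmer to add the option.

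A reader might also infer that the excess grows with missing data, since the gap between critical values does. It does not: the inflated standard error offsets part of the gap, and the calculated level drifts from 5.28% at 0% to 5.21% at 20%. Nor does EDF= restore exactly 5.0%; at 20% missing it is slightly conservative.

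Finally, this is a Phase 2 proof-of-concept study, and SAP 1 says that the Week 26 analysis does not affect the study's progression. That limits the consequence but does not remove the omission.

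**Conclusion.** The point holds as an unspecified degrees-of-freedom rule and an incomplete pooling call. Run as printed, the primary 90% interval would be about 1-2% too narrow and the one-sided level about 5.1-5.3%, an excess of roughly 0.1-0.3 percentage points. Only a p-value within about 0.003 of 0.05 could change sides, so this is minor.

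The omission itself is certain; what the final program will contain is not known. The size rests on 60 analysed per cohort, 4 parameters, 0-20% missing in equal proportions by arm, matching imputation and analysis models, and the procedure's known default.

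**What to change.** In the PROC MIANALYZE statement of SAP 6.4.1, set EDF= to the residual degrees of freedom of the ANCOVA actually fitted. That is 56 if 60 are analysed with 4 parameters; take it from the model, because enrolment is approximate and the per-protocol and COVID-19-modified sets may be smaller. Add ALPHA=0.1 so that the output is the 90% interval of 5.3.2 and not the procedure's default 95% interval. Carry both options into 6.4.4, 6.4.5 and any other analysis pooled this way, and add one sentence to 5.3.2 stating the small-sample rule (Barnard-Rubin, using the ANCOVA residual degrees of freedom).

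The cost is two code options and one sentence, with no change to design, estimand or data collection. The interval becomes about 2% wider than the printed code would give, and the test runs at about 4.7-4.9% if missingness is near 20%.

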6.4.2. SAS Code for MMRM Analysis

The secondary endpoint of percentage change from baseline to Week 50 in proteinuria utilizes MMRM analysis. Other secondary endpoints assessing longitudinal changes will also utilize MMRM analysis. Sample code is provided below:

Step 1: Impute data on or after receipt of additional standard-of-care therapy (LN cohort only) using the value collected at the time of renal flare, extrarenal SLE flare, or suboptimal response, if applicable

Step 2: Analyze imputed dataset using MMRM analysis

```
proc mixed data=ADEF method=reml;
  class subjid trt01pn avisitn strat;
  model chg= trt01pn avisitn trt01pn*avisitn base strat /ddfm=kr solution;
  repeated avisitn/type=un subject=subjid;
  lsmeans trt01pn *avisitn/cl diff;
run;
```

where subjid is the patient identifier variable, trt01pn is the randomized treatment group, avisitn is the visit variable, base is the log(proteinuria) value at baseline, strat is the randomization stratification variable and chg is the change from baseline in log(proteinuria).

6.4.3. SAS Code for Multiple Imputation

For the primary analysis of the primary endpoint, responses after treatment discontinuation will be imputed using a multiple imputation approach assuming the data are MAR and using a regression model. Sample code is provided below:

Step 1: Imputation using a monotone regression model at Week X

```
proc mi data=ADEF out=outmi seed=123 n impute=1000;  
  class trt01pn strat;  
  var trt01pn base strat Week26;  
  monotone reg(/details);  
run;
```

where trt01pn is the randomized treatment group, base is the log(proteinuria) value at baseline, strat is the randomization stratification variable, and Week 26 is the change from baseline in log(proteinuria) at Week 26.

6.4.4. SAS Code for Placebo-based Imputation

A sensitivity analysis for the primary endpoint will be performed using placebo-based imputation for responses after treatment discontinuation. In this analysis, data occurring after treatment discontinuation will be set to missing and multiple imputation will then be performed, using a regression method obtained only from placebo-treated participants with terms for baseline value and the randomization stratification variable.

The following is a partial SAS code for the placebo-based pattern imputation at Week 26:

```
proc mi data=ADEF out=outmi seed=123 n impute=1000;  
  class trt01pn strat;  
  var base strat Week26;  
  monotone reg(/details);  
  mnar model (Week26/modelobs=(trt01pn='Placebo'));  
run;
```

where trt01pn is the randomized treatment group, base is the log(proteinuria) value at baseline, strat is the randomization stratification variable, and Week26 is the change from baseline in log(proteinuria) at Week 26.

The 1000 imputed data sets are then analyzed using ANCOVA (refer to Section 6.4.1 for the SAS code), and the PROC MIANALYZE procedure will be used to generate valid statistical inferences about these parameters.

6.4.5. SAS Code for Tipping Point Sensitivity Analysis

A sensitivity analysis for the primary endpoint will be performed using the tipping point approach where a search is conducted for a tipping point that reverses the study conclusion from being favorable to ravulizumab to being unfavorable. For the tipping point sensitivity analysis, the missing data mechanism for the missing change from baseline in log proteinuria values at Week 26 will be considered to be missing-not-at-random (MNAR). Imputations are performed for missing change observations for the ravulizumab treated patients assuming not the full treatment effect, but the treatment effect adjusted by a shift parameter delta. After obtaining complete data sets for multiple shift parameters, the complete data sets will be used in the MMRM analysis, and inferences from each complete dataset will be combined using SAS PROC MIANALYZE to obtain an overall test statistic for each shift value. Multiple shift parameters will be tested until the inference concludes that statistical significance disappears.

The following is a partial SAS code for the multiple imputation analysis for a specified shift parameter at Week 26:

```
proc mi data=ADEFF out=outmi seed=123 n impute=1000;
  class trt01pn strat;
  monotone method=reg ;
  var trt01pn strat base Week26;
  mnar adjust (Week 26 /shift=delta adjustobs=(trt01pn='Ravulizumab'));
```

where trt01pn is the randomized treatment group, base is the log(proteinuria) value at baseline, Week26 is the change from baseline in log(proteinuria), and strat is the randomization stratification.

The 1000 imputed data sets are then analyzed using ANCOVA (refer to Section 6.4.1 for the SAS code), and the PROC MIANALYZE procedure will be used to generate valid statistical inferences about these parameters.

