Sample size calculations are based on a 1-sided, 2-sample t-test of log-transformed proteinuria values. The log change from baseline in proteinuria is calculated as $\log(0.85)$ and $\log(0.55)$ for the placebo and ravulizumab treatment groups, respectively, for the IgAN cohort and as $\log(0.60)$ and $\log(0.40)$ for the placebo and ravulizumab treatment groups, respectively, for the LN cohort. A common standard deviation (SD) of log change is assumed to be 0.60 ([Fellstrom, 2017](#)). Under these assumptions and an anticipated 10% drop out rate, a sample size of 60 participants (40 participants randomized to ravulizumab, 20 participants randomized to placebo) will provide approximately 80% power to detect a treatment difference with a 1-sided significance level of 0.05 in each cohort.

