- Tipping point analysis: An additional sensitivity analysis will be performed based on the delta-adjusted stress testing method (tipping point analysis). This approach assumes that patients who discontinue from ravulizumab treatment or who receive additional standard-of-care therapy (for the LN cohort only) experience worsening, defined by a prespecified adjustment (delta) in the primary efficacy endpoint compared with the observed efficacy score of patients that continue the study to next visit. For each value of delta, the treatment effect will be determined, and the value of delta for which the nominal 2-sided p-value crosses 0.10, will be considered as the ‘tipping point’ in the sense that the conclusion drawn from the primary analysis is reversed when patients who drop out or who receive additional standard-of-care therapy are assumed to experience this fixed adjustment after the discontinuation visit or receipt of additional standard-of-care therapy. After such a tipping point is determined, clinical judgment will be applied as to the plausibility of the assumptions underlying this tipping point. This methodology is expected to inform what it would take to overturn study conclusions based on varying assumptions about missing data ([Ratitch, 2013](#); [Ratitch, 2014](#)).
- Per-randomized stratification analysis: The primary endpoint will be analyzed in the same manner as the primary analysis, except using per-randomized stratification factor from IXRS in the analysis.

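### The tipping-point text worsens rescued LN participants by delta, but the procedure and code in SAP 6.4.5 shift only missing ravulizumab values, so as specified the rescue assumption would go untested

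*SAP*

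**What the plan says.** In this note, rescue means receipt of additional standard-of-care therapy in the LN cohort.

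- **Stated assumption.** SAP 5.3.3 describes the tipping-point analysis as follows: "This approach assumes that patients who discontinue from ravulizumab treatment or who receive additional standard-of-care therapy (for the LN cohort only) experience worsening". The tipping row of Table 2 likewise assumes that rescued participants do worse than comparable participants who were not rescued. The tipping point is "the value of delta for which the nominal 2-sided p-value crosses 0.10".
- **Stated procedure.** SAP 6.4.5 limits the shift: "Imputations are performed for missing change observations for the ravulizumab treated patients assuming not the full treatment effect". Its code applies the MNAR shift to Week 26 in the ravulizumab arm and carries no rescue flag.
- **Handling of rescued values.** For the primary endpoint, SAP 5.1.4 carries the flare-time 24-hour value forward. SAP 6.4.1 does this before multiple imputation: "Impute data on or after receipt of additional standard-of-care therapy (LN cohort only) using the value collected at the time of renal flare".
- **Analysis model.** SAP 6.4.5 says "the complete data sets will be used in the MMRM analysis", but its closing paragraph sends the imputed data sets to ANCOVA. Table 2 also says ANCOVA.

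**The concern.** PROC MI with MNAR ADJUST moves imputed values. It leaves values already present alone. A rescued participant whose Week 26 value has been filled with the flare value is therefore untouched by delta, although 5.3.3 says that participant is worsened.

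Every other analysis in Tables 2 and 3 keeps the flare-value fill, except the treatment-policy analysis, which uses observed data and adds no worsening. The tipping point is thus the only delta-based stress test of how rescue is handled in LN. If it shifts discontinuers alone, the reported delta answers a narrower question than the one 5.3.3 poses, and the table will not show this.

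**Working it through.** **1. Text against code (ravulizumab arm, LN)**

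| Source | Discontinued | Rescued |
|---|---|---|
| SAP 5.3.3 and Table 2, tipping row | worsened by delta | worsened by delta |
| SAP 5.1.4 and 6.4.1, Steps 1 and 2 | imputed | flare value carried forward, so present |
| SAP 6.4.5 text and code | imputed and shifted | shifted only if missing |

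**2. Does any stated rule make rescued values missing here?** None does. With the fill they are present. Without it, Protocol 3.2.4 lets these participants stay in the study, so a Week 26 value would normally be observed. The SAP writes a set-to-missing rule where it wants one: 6.4.4 for post-discontinuation data, and 5.4.1 and 5.4.2 for post-rescue data in the second MMRM. SAP 6.4.5 has none.

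**3. Inputs for size.** The SAP gives no delta grid or tipping value, so there is no plan figure to reproduce. The threshold is coherent: two-sided 0.10 equals the primary test ("Hypothesis testing will be one-sided and performed at the 0.05 level of significance"). From SAP section 3:
- LN log changes are set "as $\log(0.60)$ and $\log(0.40)$ for the placebo and ravulizumab treatment groups, respectively, for the LN cohort", a difference of log(0.40/0.60) = -0.405, or GMR 0.667.
- "A common standard deviation (SD) of log change is assumed to be 0.60".
- Allocation is 40:20. The 10% dropout is taken as 4/40 and 2/20 discontinuers.

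Rescue rates and flare levels are my assumptions; the documents give neither.

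**4. First-order ratio.** The shift in the ravulizumab mean is delta times the fraction shifted. Let r be the rescued fraction. Filled and unshifted moves 0.10 of the arm; filled and shifted moves 0.10 + r. The ratio of tipping deltas is (0.10 + r)/0.10:
- r = 0.05: 0.15/0.10 = 1.5
- r = 0.10: 0.20/0.10 = 2.0

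**5. Simulation.** LN trials were simulated with the inputs above, regression multiple imputation (30 imputations), ANCOVA on treatment and baseline, and Rubin pooling, with a search on delta to two-sided p = 0.10. There were 60 data sets per scenario. The stratum term was omitted and rescued participants were drawn at random. Delta is applied to ravulizumab rows only.
- A: rescued values filled, not shifted
- B: rescued values filled, then shifted
- C: rescued values set to missing, imputed and shifted

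Median tipping delta (log scale):

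| Rescued (ravulizumab; placebo) | Flare value | GMR | A | B | C | A/B |
|---|---|---|---|---|---|---|
| 0/40; 0/20 | none | 0.667 | 0.93 | 0.93 | 0.87 | 1.0 |
| 2/40; 1/20 | baseline | 0.667 | 0.76 | 0.50 | 0.68 | 1.5 |
| 2/40; 1/20 | 75% above | 0.667 | 0.67 | 0.40 | 0.72 | 1.7 |
| 4/40; 2/20 | baseline | 0.667 | 0.47 | 0.21 | 0.38 | 2.2 |
| 4/40; 4/20 | baseline | 0.667 | 1.00 | 0.47 | 0.41 | 2.1 |
| 4/40; 2/20 | baseline | 0.50 | 2.27 | 1.15 | 1.59 | 2.0 |
| 4/40; 2/20 | 75% above | 0.667 | 0.12 | 0.05 | 0.41 | both near 0 |
| 8/40; 4/20 | 75% above | 0.667 | 0.00 | 0.00 | 0.22 | both 0 |

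A was never below B, and A/B follows the first-order ratio. A against C goes both ways: 1.00 against 0.41, but 0.12 against 0.41. With no rescue, A and C differ only through imputation draws (0.93 and 0.87), so A-to-C gaps below about 0.1 should not be interpreted.

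**The case against.** The strongest reply is that nothing in 6.4.5 says the rescued values are filled. The fill is Step 1 of the primary ANCOVA flow, and 6.4.5 refers to 6.4.1 only for the ANCOVA code. In Table 2 the placebo-based and per-randomized rows state the flare-value rule, while the tipping row leaves it out. The code is also labelled partial. If post-rescue values were set to missing, it would shift rescued ravulizumab participants as 5.3.3 describes. This stands to the extent that a coding error is not proven: that the values are already filled is an inference from the general handling of the endpoint. It does not remove the conflict, because the step that would reconcile the two sections is not written.

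A reader might also infer that robustness is overstated, by a fixed factor of 2 or more. The documents do not support that. The factor compares A with B, depends on a rescue rate they do not give, and does not carry over to C. A carried-forward flare value is itself unfavourable and is applied to placebo as well. A level 75% above baseline is not contrived, since that rise is one component of a Renal Flare route in Protocol 3.2.1. Rescue for Suboptimal Response is possible only after Week 26 (Protocol 3.2.3 and 6.6), which limits rescue before the primary endpoint.

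Nor is the tipping point the only analysis that varies rescue handling. The treatment-policy analysis in SAP 5.3.4 uses observed post-rescue data, and SAP 5.4.1 runs the Week 50 proteinuria MMRM two ways. Neither applies a worsening. The MMRM wording is probably an editorial slip.

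**Conclusion.** The point holds as a conflict between the assumption in SAP 5.3.3 and Table 2 and the procedure in 6.4.5. Followed as written, the SAP would not give rescued LN participants a delta, and the described stress test of rescue would not be delivered.

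Relative to filling and shifting, leaving filled values unshifted gives a tipping delta at least as large, and about 1.5 to 2 times larger with 5% to 10% of the ravulizumab arm rescued and 10% discontinued. Relative to setting to missing, imputing and shifting, the sign is not fixed. The effect is nil if no ravulizumab participant is rescued before Week 26. The primary test is unaffected; this concerns one sensitivity analysis of the LN cohort. The contradiction between MMRM and ANCOVA within 6.4.5 holds without conditions.

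**What to change.** In SAP 6.4.5, before the LN Week 26 data are unblinded to the study team, define the tipping-point data set so that the code matches 5.3.3:

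- **(a)** Set post-rescue Week 26 values to missing, so that PROC MI imputes and shifts them together with discontinuations. This fits the comparison with similar unrescued participants in Table 2.
- **(b)** Alternatively, keep the flare value and add delta after imputation to flagged rescued ravulizumab rows.

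Reporting both is preferable, because (a) can be the less conservative when flare values are high. State how rescued placebo participants are handled: the code shifts ravulizumab only, while the Table 2 row is not limited to one arm. Replace MMRM with ANCOVA in the 6.4.5 text.

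The cost is a few lines of code and text, plus a second set of tipping results if both are reported. The reported tipping delta may move in either direction.
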